### **3. Distinctive Features and Innovations**

3.1 Theoretical Innovation: Identifies and corrects reasons for unimproved blood pressure after CPAP therapy, thereby increasing benefits for OSA patients.

3.2 Technical Innovation: Develops a sleep-blood pressure index through synchronized continuous blood pressure and sleep monitoring, providing a new indicator for cardiovascular risk assessment in OSA patients.

#### **4. Key Scientific Questions:**

Scientific Question 1: How can we predict which individuals are likely to benefit from CPAP therapy before treatment initiation?

Solution: Administer an innovative sleep-blood pressure index to patients with moderate-to-severe OSA and initiate CPAP therapy, demonstrating that the sleep-blood pressure index can predict blood pressure improvement following CPAP treatment.

Scientific Question 2: Why is blood pressure improvement limited in OSA patients after CPAP therapy?

Solution: Investigate the relationship between sleep parameters and clinical improvements post-CPAP therapy, identifying insomnia and arousal as key factors limiting treatment benefits in OSA patients.

Scientific Question 3: How can we enhance blood pressure benefits in OSA patients following CPAP therapy?

Solution: Improve CPAP adherence by administering sleep aids to specific patient groups, thereby increasing blood pressure benefits in OSA patients.

### **III. Research Protocol and Technical Approach**

1. Study Design: Through a cohort study, this research aims to: ① explore innovative sleep-blood pressure indices; ② elucidate factors influencing suboptimal blood pressure improvement following CPAP therapy in OSA patients; ③ determine whether sleep aids alleviate insomnia and awakenings, thereby enhancing CPAP compliance and improving blood pressure.
2. Study Population: Participants will be recruited from the Sleep Medicine Center and Hypertension Department of Anzhen Hospital.

#### **(1) Inclusion Criteria:**

- Aged 18–70 years;
- Diagnosed with obstructive sleep apnea (OSA) via overnight polysomnography (PSG), meeting either: (a) AHI  $\geq 5$  events/hour with at least one of the following: (1) patient-reported daytime sleepiness, unrefreshing sleep, fatigue, or insomnia; (2) sleep arousal due to gasping or choking; (3) Reports from bed partners or witnesses of habitual snoring, breathing interruptions, or both during sleep. Or (b) AHI  $\geq 15$  events/hour.
- Blood pressure meeting any of the following criteria: (1) Office BP 120-139/80-89 mmHg with  $\leq 2$  cardiovascular risk factors; (2) Newly diagnosed blood pressure 140-159/90-99 mmHg without cardiovascular risk factors; (3) Hypertensive patients with low cardiovascular risk who are currently on stable antihypertensive medication but whose office blood pressure does not meet normal blood pressure standards (120/80 mmHg); (4) Any non-high cardiovascular risk patient who voluntarily requests three months of non-antihypertensive medication therapy;
- Able to tolerate 24-hour ambulatory blood pressure monitoring and continuous blood pressure monitoring;
- Understands and signs the informed consent form, voluntarily agrees to undergo 3 months of

CPAP therapy and participate in follow-up visits.

**(2) Exclusion Criteria:**

- Previously diagnosed OSA currently undergoing treatment (CPAP, orthodontic appliances, surgery, etc.);
- Secondary hypertension caused by factors other than OSA, such as renal artery stenosis, nephropathy, Cushing's syndrome, or primary aldosteronism;
- Unstable medical condition (cardiovascular or cerebrovascular events or major surgery within the past 3 months, severe hypersomnia [ESS  $\geq$  16 points] or cognitive impairment preventing cooperation, active psychiatric illness, or substance/alcohol abuse);
- Rheumatic/autoimmune diseases and malignancies;
- Aortic diseases (e.g., giant cell arteritis, aortic dissection, aneurysms);
- Conditions preventing accurate blood pressure measurement (e.g., atrial fibrillation, upper limb vascular disease);
- Familial early-onset hypertension;
- Use of any prescription or over-the-counter sleep aids within 4 weeks prior to enrollment (e.g., benzodiazepines, non-benzodiazepine hypnotics, melatonin receptor agonists, trazodone, sedative antidepressants/antipsychotics, sedative-containing OTC products);
- Allergy or contraindication to potential study drugs (trazodone, zopiclone);
- Pregnancy, lactation, or planned pregnancy;
- Frequent night shift work ( $\geq$ 3 nights/week) or diagnosed circadian rhythm disorder;
- Participation in other interventional clinical trials.

3. CPAP Intervention: Subjects undergo CPAP therapy in fixed pressure mode, with  $\geq$ 4 hours of use

per night and  $\geq 21$  days of use per month. Prior to treatment initiation, subjects undergo overnight automatic (or manual) pressure titration under PSG or overnight automatic pressure titration without PSG, based on clinical condition, to select the optimal pressure achieving “optimal/good” therapeutic effect (referencing the American Academy of Sleep Medicine's CPAP Treatment and Titration Standards for Adult Obstructive Sleep Apnea). Investigators enhance subjects' understanding of CPAP through educational outreach to overcome psychological barriers. During follow-up, respiratory and otolaryngology specialists addressed specialty-related issues affecting CPAP use, promptly resolving CPAP-related discomforts to enhance CPAP adherence.

4. Pharmacological Intervention: For patients with OSA and insomnia selected in Study Component 3, or those experiencing frequent awakenings despite CPAP therapy, combined CPAP and trazodone (or zopiclone) treatment was recommended. The treatment regimen involves taking trazodone at an initial dose of 25-50 mg/night before bedtime. Based on patient tolerance and efficacy, the dose may be increased by 25 mg every 3-5 days, not exceeding a maximum of 150 mg/night. Zopiclone should start at 3.75-7.5 mg/night, adjustable to 7.5 mg/night as appropriate. The total treatment period was 4 weeks. Changes in subjective and objective sleep quality before and after medication were recorded using questionnaires, actigraphs, and polysomnography. During follow-up, patients were naturally grouped based on treatment choice and adherence: CPAP alone, CPAP plus trazodone, trazodone alone, and untreated. Compare baseline-to-endpoint blood pressure changes across groups, including intra-group comparisons and inter-group comparisons of rate of change.

5. Sample Size Estimation: Based on the research team's preliminary findings, this project will enroll 120 OSA patients receiving CPAP therapy (Research Content 1-2) and 80 patients with insomnia combined with OSA or frequent awakenings during CPAP use (Research Content 3).

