### **(3) Sleep aids may improve sleep quality and enhance CPAP compliance, potentially increasing blood pressure benefits**

Numerous studies indicate that CPAP usage duration is one of the most critical factors determining cardiovascular benefits in patients with obstructive sleep apnea. However, many OSA patients also suffer from severe insomnia, making it difficult for them to tolerate CPAP therapy. At the same time, some OSA patients experience a lowered arousal threshold after CPAP treatment, Difficulty falling asleep and early morning awakenings significantly impair CPAP treatment adherence.

Therefore, insomnia and awakenings may be factors affecting CPAP treatment compliance, thereby reducing blood pressure benefits in OSA patients. Recent studies indicate that trazodone reduces post-CPAP awakenings and improves CPAP treatment adherence, Therefore, we hypothesize that administering sleep aids to OSA patients experiencing insomnia and wakefulness may improve sleep quality following CPAP therapy, enhance CPAP compliance, and potentially increase blood pressure benefits.

This study will conduct a cohort analysis involving patients with early-stage blood pressure abnormalities who have not received drug therapy, as well as hypertensive patients requesting non-pharmacological blood pressure management.

The objectives are: ① to identify OSA patients likely to benefit from blood pressure control using

an innovative sleep-blood pressure index; ② to examine the impact of insomnia and arousal following CPAP therapy on blood pressure; ③ to enhance sleep quality with sleep aids, thereby improving CPAP treatment adherence and blood pressure outcomes. This study will provide novel insights and solutions to address the challenge of uncontrolled blood pressure following CPAP therapy for OSA.

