## **II. Research Objectives and Content**

### **1. Research Objectives**

1.1 Validate innovative sleep-blood pressure parameters for screening OSA patients who benefit from blood pressure improvement after CPAP therapy.

1.2 Identify reasons for suboptimal blood pressure improvement in OSA patients after CPAP therapy through analysis of treated patients.

1.3 Improve CPAP treatment compliance and enhance blood pressure benefits by administering trazodone or zopiclone for insomnia and post-CPAP arousals (including micro-arousals).

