### **2. Research Content**

2.1 Screen OSA patients likely to benefit using an innovative sleep-blood pressure index: Develop the sleep-blood pressure index by precisely measuring continuous blood pressure via novel volumetric clamping technology and synchronizing it with PSG through engineering techniques. Conduct a cohort study to analyze characteristics of patients with blood pressure improvement after CPAP therapy, obtaining a sleep-blood pressure index and its cutoff value for predicting CPAP treatment benefits.

2.2 Exploring Factors Influencing Blood Pressure Improvement After CPAP Therapy: Compare differences in sleep-related parameters—including insomnia indices, arousal-related indices, and autonomic function—between patients with and without blood pressure improvement after 3 months of CPAP therapy. Analyze residual sleep factors affecting CPAP efficacy.

2.3 Enhancing CPAP Compliance and Blood Pressure Benefits in OSA Patients: Select patients with pre-CPAP insomnia or frequent post-CPAP arousals. Administer trazodone or zopiclone for 4 weeks alongside CPAP therapy. Demonstrate how sleep aids improve sleep quality in OSA patients, thereby increasing CPAP compliance and enhancing blood pressure outcomes.

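### Component 3 compares blood pressure change across groups defined partly by adherence, which the sleep aid is meant to change, so the comparison cannot support the causal wording of the aim

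*Protocol*

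**What the plan says.** Section III, item 4 (Pharmacological Intervention) concerns patients with OSA and insomnia, or with frequent awakenings despite CPAP. For them, "combined CPAP and trazodone (or zopiclone) treatment was recommended". It then sets the grouping rule: "During follow-up, patients were naturally grouped based on treatment choice and adherence: CPAP alone, CPAP plus trazodone, trazodone alone, and untreated". The next sentence gives the analysis: "Compare baseline-to-endpoint blood pressure changes across groups", both within and between groups. Item 5 plans 80 patients for this component and 120 CPAP patients for Research Content 1-2.

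The aim is worded causally, and CPAP compliance is part of the effect sought:

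- Objective 1.3: "Improve CPAP treatment compliance and enhance blood pressure benefits by administering trazodone or zopiclone".
- Research Content 2.3: "Demonstrate how sleep aids improve sleep quality in OSA patients, thereby increasing CPAP compliance and enhancing blood pressure outcomes".
- Key Scientific Question 3: "Improve CPAP adherence by administering sleep aids to specific patient groups, thereby increasing blood pressure benefits in OSA patients".
- Section III, item 1, aim 3: "determine whether sleep aids alleviate insomnia and awakenings, thereby enhancing CPAP compliance and improving blood pressure".

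Expected result 2 (section IV) also has the drugs lowering daytime blood pressure through better sleep and fewer awakenings during CPAP. The background, section I(3), is more cautious and offers the chain as a hypothesis: "enhance CPAP compliance, and potentially increase blood pressure benefits".

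**The concern.** Adherence has two roles in this plan: the drug is meant to improve it, and it helps decide which group a patient is counted in. A comparison within levels of something the treatment changes no longer compares like with like, even if the groups were alike at the start. Part of any true benefit is hidden, and a benefit can appear where there is none.

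This is the between-group comparison described for Component 3, so what can be concluded about objective 1.3 depends on it. The protocol itself fixes the rule. A statistical analysis plan could define an adherence threshold or add covariates, but it could not remove the problem without redefining the groups.

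**Working it through.** The protocol gives no figure to reproduce here. It states no adherence threshold, expected CPAP use or effect size. The logic comes first, then a scale based on assumed inputs.

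**Two readings of adherence**

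- *CPAP use.* A patient on CPAP and trazodone who abandons CPAP leaves the combined group. The drug's effect on CPAP use helps decide who stays, so patients are sorted on a consequence of treatment.
- *Drug use.* A patient who stops the drug moves to CPAP alone. That group then mixes patients who never took the drug with those who gave it up.

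Both readings use events after the drug starts.

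**Scale, reading 1 (CPAP use)**

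Assumed: nightly CPAP use has mean μ = 4 h without the drug and 5 h with it (a lift of 1 h), SD σ = 2 h, floored at 0; 1 mmHg lower per hour; groups equal at the start. Φ and φ are the standard normal distribution and density functions.

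Mean hours with everyone kept in the group they started: μΦ(μ/σ) + σφ(μ/σ). This gives 4.017 and 5.004 h, a difference of 0.987 h, or 0.99 mmHg.

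Mean hours among those above a cut c: μ + σφ(a)/(1 − Φ(a)), with a = (c − μ)/σ.

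| Cut | Without drug | With drug | Difference | Share hidden, 1 − difference/0.987 |
|---|---|---|---|---|
| Any use | 4.110 h | 5.035 h | 0.925 h | 6% |
| 2 h | 4.575 h | 5.278 h | 0.702 h | 29% |
| 4 h | 5.596 h | 6.018 h | 0.423 h | 57% |

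The 4 h figure appears in the CPAP regimen (section III, item 3), but the grouping rule does not use it. The shares refer only to the effect that runs through adherence. If better sleep lowers blood pressure by a further 1 mmHg directly, the 4 h cut hides (1.987 − 1.423)/1.987 = 28% of the total. With a further 2 mmHg it hides (2.987 − 2.423)/2.987 = 19%.

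**Scale, reading 2 (drug use only)**

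Assumed: no drug effect; equal numbers start with and without the drug; choice unrelated to motivation; a share q stops; keeping the drug correlates 0.4 with motivation; motivation correlates 0.4 with CPAP hours. Through hours alone, motivation is worth 0.4 × 2 h × 1 mmHg = 0.8 mmHg per SD. Let b be any further fall per SD by other routes.

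The gap in motivation between keepers and the enlarged CPAP-alone group is 0.4 × φ(z_q) × [1/(1 − q) + 1/(1 + q)], where z_q is the normal quantile of q:

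- q = 0.15: 0.4 × 0.2332 × 2/0.9775 = 0.191 SD
- q = 0.30: 0.4 × 0.3477 × 2/0.91 = 0.306 SD

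False benefit = gap × (0.8 + b):

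| b (mmHg per SD) | q = 0.15 | q = 0.30 |
|---|---|---|
| 0 | 0.15 | 0.24 |
| 1 | 0.34 | 0.55 |
| 2 | 0.53 | 0.86 |
| 3 | 0.73 | 1.16 |

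With everyone kept in the group they started, the false benefit is 0. The input b drives the result.

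**Choice at the start**

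If choice correlates r with motivation and half choose the drug, the gap is 4 × r × φ(0) = 4 × r × 0.3989: 0.319 SD at r = 0.2 and 0.638 SD at r = 0.4. With no drug effect and groups fixed at the start, the false benefit is 0.319 × 0.8 = 0.26 mmHg (r = 0.2, b = 0) up to 0.638 × 3.8 = 2.43 mmHg (r = 0.4, b = 3). If the patients who accept the drug have the worse outlook, r is negative and the same amounts count against the drug.

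**The case against.** Much of the case on the other side stands.

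- *This is openly a cohort study, and choice can be a baseline exposure.* Agreed. A reader might infer that every patient is sorted on events after the start. The text does not show that. Patients with awakenings on CPAP necessarily reach the drug decision during CPAP follow-up, so the timing phrase does not prove sorting after the drug. Only adherence clearly does.
- *The comparison groups need not be refusers.* All participants agree to CPAP and the combination is recommended, so a reader might infer that the other three groups are all decliners or non-adherers. The protocol does not say so. Patients from the 120 of Research Content 1-2 could supply CPAP alone.
- *The sleep-quality link is measured separately.* Agreed. Questionnaires, actigraphy and polysomnography before and after medication do not depend on the four groups. They are uncontrolled, but the grouping sentence does not harm them.
- *The biases do not have a known direction.* Agreed. One might infer that hidden benefit and self-selection pull in opposite ways. That fails if patients with worse insomnia accept the drug more often, since expected result 2 links insomnia to poorer blood pressure response.
- *The numbers rest on assumptions.* Agreed. The hidden share runs from 6% to 57% on the choice of cut alone, and the false benefit depends mainly on b.

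None of this rescues adherence as a grouping variable alongside causal wording.

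**Conclusion.** The concern holds for adherence. Whichever adherence is meant, the groups depend on what happens after the drug starts, and CPAP compliance is an effect the drug is intended to have. The between-group blood pressure comparison therefore cannot support the causal verbs of Research Content 2.3 and design aim 3 for compliance and blood pressure.

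Direction and size are unknown. Under the assumptions above, 6% to 57% of the adherence-mediated effect is hidden if CPAP use sorts the patients. If drug use sorts them, the false benefit is about 0.15-0.24 mmHg when motivation acts only through CPAP hours, and 0.3-1.2 mmHg when it also lowers blood pressure by 1-3 mmHg per SD. The conclusion rests on the logic of the rule, not on these figures.

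It would go too far to say that regrouping makes the comparison causal. Choice bias remains and can be larger than the bias removed.

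A minor point in the same sentence: the group labels name only trazodone, although zopiclone is also a study drug. The labels may be shorthand, but the passages must be reconciled.

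**What to change.** Replace the grouping sentence with: *Groups are fixed by the treatment decision recorded at the visit at which the sleep aid is offered; patients are analysed in that group whatever their later adherence to CPAP or drug.* In addition:

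- State whether patients from the 120 of Research Content 1-2 may serve as CPAP alone.
- Make CPAP plus sleep aid versus CPAP alone the main contrast, and report the other groups descriptively.
- Analyse CPAP use as an outcome, and keep adherence-defined groups as description only.
- Take baseline blood pressure at or before that visit, and use one stated endpoint time for both groups.
- Adjust for baseline blood pressure, insomnia severity, entry route (insomnia before CPAP or awakenings on CPAP) and, where it exists, earlier CPAP use.
- State that choice bias remains, is not cured by regrouping and can exceed the bias removed.
- Word objective 1.3, content 2.3, design aim 3 and expected result 2 as associations. Keeping the causal wording would need random allocation of the sleep aid, which is a different design.

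The cost is protocol wording, a modelling step and possibly one added blood pressure reading. Estimates may look less favourable because non-adherers stay in their group, and fewer of the 80 enter the main contrast. With an assumed SD of change of 8 to 12 mmHg, the 95% half-width runs from 1.96 × 8 × √(2/40) = 3.5 mmHg (40 per group) to 1.96 × 12 × √(2/20) = 7.4 mmHg (20 per group). A difference of 1 mmHg could not be seen, which is a further reason for modest wording.

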## **IV. Expected Outcomes and Evaluation Metrics**

### **(1) Expected Results**

1. The Sleep-Blood Pressure Index can predict the efficacy of blood pressure improvement following CPAP therapy, identifying OSA patients likely to benefit from CPAP treatment.
2. Insomnia and awakenings (including micro-awakenings), along with the resulting sympathetic overactivation, are key factors contributing to suboptimal blood pressure improvement after CPAP. Trazodone and zopiclone improve sleep quality, reduce awakenings and blood pressure fluctuations during CPAP therapy, thereby lowering daytime blood pressure values.

### **(2) Evaluation Metrics**

1. Propose and validate an innovative sleep-blood pressure metric.
2. Publish two SCI papers (Q1 and Q2 journals).

This protocol strictly adheres to the Good Clinical Practice (GCP) guidelines and Anzhen Hospital's Special Management Measures for High-Level Research. It integrates all technical details of the application and has mitigated common risks of ethical rejection (funding disclosure, vulnerable subject protection, and intervention rationale).
